5.1.1 Retesting During Screening

Any new result will override the previous result (i.e., the most current result prior to Randomization) and is the value by which study inclusion will be assessed, as it represents the subject's most current, clinical state.

5.2 Study Materials

- NCI CTCAE version 4.0
- BMS-936558 (nivolumab) IB
- Ipilimumab IB
- Pharmacy Information Sheets
- Laboratory manuals for collection and handling of blood (including biomarker and immunogenicity) and tissue specimens
- Site manual for operation of IRT, including enrollment worksheets
- Manual for entry of local laboratory data
- Serious Adverse Events (or eSAE) case report form pages
- Pregnancy surveillance forms
- RECIST 1.1 pocket guide
- Quality of Life questionnaires.

5.3 Safety Assessments

At baseline, a medical history will be obtained to capture relevant underlying conditions. The baseline examinations should include weight, height, ECOG Performance Status, blood pressure (BP), heart rate (HR) and temperature should be performed within 28 days prior to randomization. Baseline signs and symptoms are those that are assessed within 14 days prior to first dose. Concomitant medications will be collected from within 14 days prior to the first dose through the study treatment period (see [Table 5.1-1](#)).

Baseline local laboratory assessments should be done within 14 days prior to the randomization and include: CBC with differential, LFTs (ALT, AST, total bilirubin, alkaline phosphatase), BUN or serum urea level, creatinine, albumin, Ca, Mg, Na, K, Cl, LDH, glucose, amylase, lipase, TSH, Free T4, Free T3, and Hep B and C testing (HBV sAg and HCV RNA or Ab) (see [Table 5.1-1](#)).

Pregnancy testing for WOCBP (done locally) must be performed within 24 hours prior to the initial administration of study drug at baseline and then every 3 weeks during Part 1, every 4 weeks during Part 2, and at the safety follow up visits (Follow up visits 1 and 2).

Subjects will be evaluated for safety if they have received any study drug. Toxicity assessments will be continuous during the treatment phase. During the safety follow-up phase ([Table 5.1-4](#)), toxicity assessments should be done in person. Once subjects reach the survival follow-up phase, either in-person visits or documented telephone calls to assess the subject's status are acceptable.

Adverse events and laboratory values will be graded according to the NCI-CTCAE version 4.0.

On-study weight, ECOG performance status, and vital signs should be assessed at each on-study visit prior to nivolumab dosing. Vital signs should also be taken as per institutional standard of care prior to, during and after dosing. The start and stop time of the nivolumab infusion should be documented. Physical examinations are to be performed as clinically indicated (including a pulmonary assessment at screening). If there are any new or worsening clinically significant changes since the last exam, report changes on the appropriate non-serious or serious adverse event page.

During Part 1, on-study local laboratory assessments should be done within 72 hours prior to each dose and include: CBC w/differential, LFTs (ALT, AST, total bilirubin, alkaline phosphatase), BUN or serum urea level, creatinine, Ca, Mg, Na, K, Cl, LDH, glucose, amylase, lipase, TSH with reflexive Free T4, Free T3 and albumin if clinically indicated.

During Part 2, on-study local laboratory assessments should be done within 72 hours prior to the first (Part 2) dose beginning at Cycle 5 (Week 18) and every alternate dose thereafter (Cycle 7, 9, 11, 13, etc) and include: CBC w/differential, LFTs (ALT, AST, total bilirubin, alkaline phosphatase), BUN or serum urea level, creatinine, Ca, Mg, Na, K, Cl, LDH, glucose, amylase, lipase, TSH with reflexive Free T4, Free T3 and albumin if clinically indicated.

During Part 2, on-study local laboratory assessment should be done within 72 hours prior to the second (Part 2) dose (beginning at Cycle 6 and every alternate dose thereafter (Cycle 8, 10, 12, 14, etc) and include: LFTs (ALT, AST, total bilirubin, alkaline phosphatase) and creatinine.

Additional measures, including non-study required laboratory tests, should be performed as clinically indicated or to comply with local regulations. Laboratory toxicities (eg, suspected drug induced liver enzyme elevations) will be monitored during the follow-up phase via on site/local labs until all study drug related toxicities resolve, return to baseline or are deemed irreversible.

Some of the previously assessments referred to in this section may not be captured as data in the eCRF. They are intended to be used as safety monitoring by the treating physician. Additional testing or assessments may be performed as clinically necessary or where required by institutional or local regulations.

5.4 Efficacy Assessments

Study evaluations will take place in accordance with the flow charts in [Section 5.1](#). Baseline assessments should be performed within 28 days prior to randomization utilizing CT or MRI. In addition to chest, abdomen, pelvis, and brain, all known sites of disease should be assessed at baseline. Subsequent assessments should include chest, abdomen, and pelvis, and all known sites of disease and should use the same imaging method as was used at baseline. Subjects will be evaluated for tumor response beginning 12 weeks (\pm 1 week) from randomization and continuing every 8 weeks (\pm 1 week) for the first 12 months and every 12 weeks (\pm 1 week) thereafter, until disease progression is documented or treatment is discontinued (whichever occurs later). Tumor assessments for ongoing study treatment decisions will be completed by the investigator using RECIST (Response Evaluation Criteria in Solid Tumors) 1.1 criteria.

Radiographic images will be collected and sent to a centralized imaging core laboratory for storage and potential future central reading.

5.4.1 Primary Efficacy Assessment

Efficacy assessment is not a primary endpoint. The primary endpoint is the incidence of drug-related Grade 3 - 5 AEs. See [Section 6](#) for a further description of adverse event reporting.

5.4.2 Secondary Efficacy Assessments

The secondary measure of efficacy will include the ORR and PFS.

The ORR, will be determined by the investigator using RECIST 1.1 criteria, in all treated subjects. ORR and is defined as the number of subjects with a BOR of complete response (CR) or partial response (PR) divided by the number of treated subjects. The investigator-determined ORR will be further characterized by the investigator-determined duration of response (DOR) and the magnitude of reduction in tumor volume

The other secondary efficacy measure will be to evaluate PFS in all treated patients.

Additional secondary endpoints include OS in all treated subjects.

Radiographic images will be collected and sent to a centralized imaging core laboratory for storage and potential future central reading.

5.4.2.1 Measurable Lesions

Measurable lesions must be accurately measured in at least one dimension (longest diameter in the plane of the measurement to be recorded) with a minimum size of:

- 10 mm by CT/MRI scan (CT/MRI scan slice thickness no greater than 5 mm)
- 10 mm caliper measurement by clinical exam (lesions which cannot be accurately measured with calipers should be recorded as nonmeasurable)
- 20 mm by chest x-ray.

Malignant lymph nodes: To be considered pathologically enlarged and measurable, a lymph node must be ≥ 15 mm in short axis when assessed by CT scan (CT scan slice thickness recommended to be no greater than 5 mm). At baseline and in follow up, only the short axis will be measured and followed.

5.4.2.2 Non-measurable Lesions

All other lesions, including small lesions (longest diameter < 10 mm or pathological lymph nodes with ≥ 10 to < 15 mm short axis), as well as truly non-measurable lesions.

- Lesions considered truly non-measurable include: leptomeningeal disease, ascites, pleural or pericardial effusion, inflammatory breast disease, lymphangitic involvement of skin or lung, abdominal masses/abdominal organomegaly identified by physical exam that is not measurable by reproducible imaging techniques.

5.4.2.3 Special Considerations Regarding Lesion Measurability

Bone Lesions

- Bone scan, PET scan, or plain films are not considered adequate imaging techniques to measure bone lesions. However, these techniques can be used to confirm the presence or disappearance of bone lesions.
- Lytic bone lesions or mixed lytic-blastic lesions, with identifiable soft tissue components, that can be evaluated by cross sectional imaging techniques such as CT or MRI can be considered as measurable lesions if the soft tissue component meets the definition of measurability described above.
- Blastic bone lesions are non-measurable.

Cystic Lesions

Lesions that meet the criteria for radiographically defined simple cysts should not be considered as malignant lesions (neither measurable nor non-measurable) since they are by definition, simple cysts.

“Cystic lesions” thought to represent cystic metastases can be considered as measurable lesions, if they meet the definition of measurability described above. However, if noncystic lesions are present in the same subject, these are preferred for selection as target lesions.

Non-measurable Lesions

Tumor lesions situated in a previously irradiated area, or in an area subjected to locoregional therapy, are usually not considered measurable unless there has been demonstrated progression in the lesion.

5.4.3 Specifications for Method of Measurement

5.4.3.1 Measurement of Lesions

All measurements should be recorded in metric notation (mm). All baseline evaluations should be performed as close as possible to the treatment start and never more than 28 days before the beginning of treatment.

5.4.3.2 Method of Assessment

The same method of assessment and the same technique should be used to characterize each identified and reported lesion at baseline and during follow-up. Imaging based evaluation should always be done rather than clinical examination unless the lesion(s) being followed cannot be imaged but are assessable by clinical exam.

5.4.3.3 CT/MRI Scan

CT/MRI is the best currently available and reproducible method to measure lesions selected for response assessment. Measurability of lesions on CT/MRI scan is based on the assumption that CT/MRI slice thickness is 5 mm or less. When CT scans have slice thickness greater than 5 mm, the minimum size for a measurable lesion should be twice the slice thickness.

5.4.3.4 Chest X-Ray

Chest CT is preferred over chest x-ray, particularly when progression is an important endpoint since CT is more sensitive than x-ray, particularly in identifying new lesions. However, lesions on chest x-ray may be considered measurable if they are clearly defined and surrounded by aerated lung.

5.4.3.5 Clinical Lesions

Clinical lesions will only be considered measurable when they are superficial and ≥ 10 mm diameter as assessed using calipers. For the case of skin lesions, documentation by color photography including a ruler to estimate the size of the lesion is suggested. As previously noted, when lesions can be evaluated both by clinical exam and imaging, imaging evaluation should be undertaken since it is more objective and may also be reviewed at the end of the study.

5.4.3.6 Ultrasound

Ultrasound is not useful in the assessment of lesion size and should not be used as a method of measurement. If new lesions are identified by ultrasound in the course of the study, confirmation by CT or MRI is advised.

5.4.3.7 Endoscopy, Laparoscopy

The utilization of these techniques for objective tumor evaluation is not advised.

5.4.3.8 Tumor Markers

Tumor markers such as, but not limited to, LDH may be used for clinical management, but will not be included in the assessment of BOR.

5.4.4 Baseline Documentation of "Target" and "Non-Target Lesions"

5.4.4.1 Target Lesions

When more than one measurable lesion is present at baseline, all lesions up to a maximum of five lesions total (and a maximum of two lesions per organ) representative of all involved organs should be identified as target lesions and will be recorded and measured at baseline.

Target lesions should be selected on the basis of their size (lesions with the longest diameter), be representative of all involved organs, and should lend themselves to reproducible repeated measurements.

A sum of the diameters (longest for non-nodal lesions, short axis for nodal lesions) for all target lesions will be calculated and reported as the baseline sum diameters. If lymph nodes are to be included in the sum, then as noted below, only the short axis is added into the sum. The baseline sum diameters will be used as reference to further characterize any objective tumor regression in the measurable dimension of the disease.

Previously treated CNS metastases are not considered measurable lesions for purposes of RECIST 1.1 determined response.

5.4.4.2 Lymph Nodes

Lymph nodes merit special mention since they are normal anatomical structures which may be visible by imaging even if not involved by tumor. Pathological nodes which are defined as measurable and may be identified as target lesions must meet the criterion of a short axis of ≥ 15 mm by CT scan. Only the short axis of these nodes will contribute to the baseline sum.

Nodes that have a short axis < 10 mm are considered non-pathological and should not be recorded or followed.

5.4.4.3 Non-target Lesions

All other lesions (or sites of disease) including pathological lymph nodes should be identified as non-target lesions and should also be recorded at baseline. Measurements are not required and these lesions should be followed as “present”, “absent”, or in rare cases “unequivocal progression”. In addition, it is possible to record multiple non-target lesions involving the same organ as a single item on the case report form (eg, “multiple enlarged pelvic lymph nodes” or “multiple liver metastases”).

5.4.5 Tumor Evaluation

Evaluation of Target Lesions

Complete Response (CR): Disappearance of all target lesions. Any pathological lymph nodes (whether target or non-target) must have reduction in short axis to < 10 mm.

Partial Response (PR): At least a 30% decrease in the sum of diameters of target lesions, taking as reference the baseline sum diameters.

Progressive Disease (PD): At least a 20% increase in the sum of diameters of target lesions, taking as reference the smallest sum on study (this includes the baseline sum if that is the smallest on study). In addition to the relative increase of 20%, the sum must also demonstrate an absolute increase of at least 5 mm. (Note: the appearance of one or more new lesions is also considered progression).

Stable Disease (SD): Neither sufficient shrinkage to qualify for PR nor sufficient increase to qualify for PD, taking as reference the smallest sum diameters while on study.

5.4.5.1 Target Lesions that Become “Too Small to Measure”

All lesions (nodal and non-nodal) recorded at baseline should have their actual measurements recorded at each subsequent evaluation, even when very small (eg, 2 mm). If the radiologist is able to provide an actual measurement, that should be recorded, even if it is below 5 mm.

5.4.5.2 Target Lesions that Split or Coalesce on Treatment

When non-nodal lesions ‘fragment’, the longest diameters of the fragmented portions should be added together to calculate the target lesion sum.

As lesions coalesce, a plane between them maybe maintained that would aid in obtaining maximal diameter measurements of each individual lesion. If the lesions have truly coalesced such that they

are no longer separable, the vector of the longest diameter in this instance should be the maximal longest diameter for the ‘coalesced lesion’.

5.4.5.3 Evaluation of Non-target Lesions

While some non-target lesions may actually be measurable, they need not be measured and instead should be assessed only qualitatively at the time points specified in the protocol.

Complete Response (CR): Disappearance of all non-target lesions. All lymph nodes must be non-pathological in size (< 10 mm short axis).

Non-CR/Non-PD: Persistence of one or more non-target lesion(s) above the normal limits.

PD: Unequivocal progression of existing non-target lesions (Note: the appearance of one or more new lesions is also considered progression).

5.4.5.4 Unequivocal Progression in Non-target Disease

To achieve ‘unequivocal progression’ on the basis of the non-target disease, there must be an overall level of substantial worsening in non-target disease such that, even in presence of SD or PR in target disease, the overall tumor burden has increased sufficiently to merit discontinuation of therapy.

A modest ‘increase’ in the size of one or more non-target lesions is usually not sufficient to qualify for unequivocal progression status.

5.4.5.5 New Lesions

The appearance of new malignant lesions denotes disease progression. The finding of a new lesion should be unequivocal: ie, not attributable to differences in scanning technique, change in imaging modality or findings thought to represent something other than tumor (for example, some “new” bone lesions may be simply healing or flare of preexisting lesions. This is particularly important when the subject’s baseline lesions show partial or complete response. For example, necrosis of a liver lesion may be reported on a CT scan reported as a “new” cystic lesion, which it is not.

A lesion identified on a follow-up study in an anatomical location that was not scanned at baseline is considered a new lesion and will indicate disease progression. An example of this is the subject who has visceral disease at baseline and while on study has a CT or MRI brain scan ordered which reveals metastases. The subject’s brain metastases are considered to be evidence of PD even if he/she did not have brain imaging at baseline.

5.4.6 Response Criteria (RECIST 1.1)

For subjects who have measurable disease at baseline, [Table 5.4.6-1](#) provides a summary of the overall response status calculation at each time point.

Table 5.4.6-1: Time Point Response - Subjects with Target (± Non-target) Disease

Target Lesions	Non-target Lesions	New Lesions	Overall Response
CR	CR	No	CR
CR	Non-CR/non-PD	No	PR
CR	Not evaluated	No	PR
PR	Non-PD or not all evaluated	No	PR
SD	Non-PD or not all evaluated	No	SD
Not all evaluated	Non-PD	No	NE
PD	Any	Yes or No	PD
Any	PD	Yes or No	PD
Any	Any	Yes	PD

CR=Complete response, PR=Partial Response, SD=Stable Disease, PD=Progressive Disease, NE=Not evaluable

5.4.6.1 Missing Assessments and Not Evaluable Designation

When no imaging/measurement is done at all at a particular time point, the subject is not evaluable (NE) at that time point. If only a subset of lesion measurements are made at an assessment, the case is also considered NE at that time point, unless a convincing argument can be made that the contribution of the individual missing lesion(s) would not have changed the assigned time-point response.

5.4.6.2 Confirmation of Scan

Verification of Response: As per RECIST 1.1, confirmation of response is required for trials with response as a primary endpoint but is no longer required in randomized studies since the control arm serves as appropriate means of interpretation of data. Hence, confirmation is NOT required.²⁷

Verification of Progression: Progression of disease should be verified in cases where progression is equivocal. If repeat scans confirm PD, then progression should be declared using the date of the initial scan. If repeat scans do not confirm PD, then the subject is considered not to have progressive disease per RECIST 1.1.

5.4.6.3 Best Overall Response

The BOR is determined once all the data for the subject is known. It is defined as the best response designation, as determined by the investigator, recorded between the date of randomization and the date of objectively documented progression per RECIST1.1 or the date of subsequent therapy, whichever occurs first. For subjects without documented progression or subsequent therapy, all available response designations will contribute to the BOR assessment. The subject's best overall response assignment will depend on the findings of both target and non-target disease and will also take into consideration the appearance of new lesions.

For the purpose of this study, the minimum scan time from baseline for determination of SD will be 12 weeks.

5.4.6.4 Duration of Objective Response

The duration of objective response is measured from the time measurement criteria are first met for CR/PR (whichever is first recorded) until the first date that progressive disease is objectively documented (taking as reference for progressive disease the smallest measurements recorded on study).

5.5 Pharmacokinetic and Immunogenicity Assessments

Samples for PK and immunogenicity assessments will be collected for all subjects receiving nivolumab and ipilimumab as described in [Table 5.5.1-1](#). All timepoints are relative to the start of study drug administration. All on-treatment timepoints are intended to align with days on which study drug is administered. If it is known that a dose is going to be delayed, then the predose sample should be collected just prior to the delayed dose. However, if a predose sample is collected but the dose is subsequently delayed, an additional predose sample should not be collected. Further details of sample collection, processing, and shipment will be provided in the laboratory procedures manual.

Blood samples should be drawn from a site other than the infusion site (ie, contralateral arm) on days of infusion. All samples collected pre-dose should be taken just prior to the administration from the contralateral arm (ie, the arm not used for the infusion). If the infusion was interrupted, the interruption details will also be documented on the CRF. Blood samples will be processed to collect serum and stored preferably at -70°C (samples may be stored at -20°C up to 2 months). Further details of pharmacokinetic sample collection and processing will be provided to the site in the lab manual.

Blood samples for immunogenicity analyses of nivolumab and/or ipilimumab will be collected according to the schedule given in [Table 5.5.1-1](#). Samples collected from subjects will be evaluated for the development of Anti-Drug Antibody (ADA) for nivolumab and/or ipilimumab by validated immunoassays. Samples may also be analyzed for neutralizing ADA response to nivolumab and/or ipilimumab. Neutralizing ADA testing conditional upon assay availability.

5.5.1 Pharmacokinetic and Immunogenicity Sample Analyses

The serum samples will be analyzed for drug (nivolumab and ipilimumab) and ADA (anti-nivolumab and anti- ipilimumab antibodies) by validated immunoassays. Samples with a positive ADA response may also be analyzed for neutralizing ADA response to nivolumab and/or ipilimumab.

In addition, selected serum samples may be analyzed by an exploratory method that measures nivolumab and ipilimumab, or detect anti-drug antibodies for technology exploration purposes; exploratory results will not be reported. The corresponding serum samples designated for either PK, immunogenicity or biomarker assessments may also be used for any of those analyses, if required (eg, insufficient sample volume to complete testing or to follow up on suspected immunogenicity related AE).

Table 5.5.1-1: Pharmacokinetic and Immunogenicity Sample Collections (CA209511)

Part ^a	Study Day ^b (1 Cycle = 3 weeks for Part 1 1 Cycle = 4 Weeks for Part 2)	Time (Event)	Time (Relative to Start of Nivolumab Infusion) Hours:Min	Pharmacokinetic Blood Sample for Nivolumab	Immunogenicity Blood Sample for Nivolumab	Pharmacokinetic Blood Sample for Ipilimumab	Immunogenic Blood Sample for Ipilimumab
1	C1D1	(Predose) ^c	00:00	X	X	X	X
1	C1D1	(EOI-nivo) ^d	00:90	X			
1	C1D1	(EOI-ipi) ^d	00:30			X	
1	C2D1	(Predose) ^c	00:00	X	X	X	X
1	C2D1	(EOI-nivo) ^d	00:90	X			
1	C2D1	(EOI-ipi) ^d	00:30			X	
1	C3D1	(Predose) ^c	00:00	X	X	X	X
1	C3D1	(EOI-nivo) ^d	00:90	X			
1	C3D1	(EOI-ipi) ^d	00:30			X	
2	C5D1	(Predose) ^c	00:00	X	X	X	X
2	C5D1	(EOI-nivo) ^d	00:30	X			
2	C9D1	(Predose)	00:00	X	X		

Table 5.5.1-1: Pharmacokinetic and Immunogenicity Sample Collections (CA209511)

Part ^a	Study Day ^b (1 Cycle = 3 weeks for Part 1 1 Cycle = 4 Weeks for Part 2)	Time (Event)	Time (Relative to Start of Nivolumab Infusion) Hours:Min	Pharmacokinetic Blood Sample for Nivolumab	Immunogenicity Blood Sample for Nivolumab	Pharmacokinetic Blood Sample for Ipilimumab	Immunogenic Blood Sample for Ipilimumab
2	CXD1: Every 16 weeks after C09 (ie, C13D1, C17D1, etc.)	(Predose)	00:00	X	X		
	First 2 Follow-up Visits (Approximately up to 100 Days from the Discontinuation of Study Drug)	NA		X	X		

^a Part 1 indicates first 12 weeks (or 4 cycles) of combination treatment (nivolumab + ipilimumab). Part 2 indicates nivolumab monotherapy period starting from Week 16 (or Cycle 5).

^b If a subject discontinues study drug treatment during the sampling period, they will move to sampling at the follow-up visits.

^c Predose: All predose samples for nivolumab and ipilimumab should be taken prior to the start of nivolumab infusion.

^d EOI-nivo and EOI-ipi: End of Infusion samples for nivolumab and ipilimumab, respectively. **For sequential dosing, both EOI samples should be collected immediately (preferably within 2 - 5 minutes) prior to the end of the ipilimumab infusion-** If the end of infusion is delayed, the collection of the EOI samples should be delayed accordingly. EIO samples may not be collected from the same IV access as drug was administered, refer to the laboratory manual for additional instructions.

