4.3.1 Part 1 Study Drug Administration (Combination Portion)

In the nivolumab plus ipilimumab combination portion, nivolumab is to be administered first. Subjects should receive nivolumab at a dose of 3 mg/kg (Arm A) or 1 mg/kg (Arm B) as a 30-minute IV infusion, on Day 1 of each treatment cycle every 3 weeks for 4 doses or until progression, unacceptable toxicity, withdrawal of consent, or the study ends, whichever occurs first.

The nivolumab infusion must be promptly followed by a saline flush to clear the line of nivolumab before starting the next infusion.

The second infusion in the combination cohort will always be ipilimumab, and will start approximately 30 minutes after completion of the nivolumab infusion and the infusion line has been flushed, filters changed and the patient has been observed to ensure no infusion reaction has occurred.

Subjects should receive ipilimumab at a dose of 1 mg/kg (Arm A) or at a dose of 3 mg/kg (Arm B) as a 30-minute IV infusion, on Day 1 of each treatment cycle every 3 weeks (within 3 calendar days of scheduled date) for 4 doses or until progression, unacceptable toxicity, withdrawal of consent, or the study ends, whichever occurs first.

The risk/benefit profile for nivolumab has primarily been investigated using a 60-minute infusion and for ipilimumab a 90-minute infusion. Long infusion times place a burden on patients and treatment centers. Establishing that these agents can be safely administered using shorter infusion times will diminish some of this burden. Previous clinical studies of nivolumab have used 60-minute infusion duration and for ipilimumab 90-minute. Both nivolumab and ipilimumab have been administered safely at doses ranging up to 10 mg/kg over these treatment durations. Overall, infusion reactions including high-grade hypersensitivity reactions have been uncommon across multiple clinical studies, and all have been managed by following the safety algorithms. Infusion duration of 30 minutes for 3 mg/kg nivolumab (30% of the dose provided at 10 mg/kg) is not expected to present any safety concerns compared with the prior experience at 10 mg/kg nivolumab dose infused over the 60-minute duration. Similarly, shortened infusion duration of 30 minutes for ipilimumab is not expected to present additional safety concerns.²⁴

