7.7 Pharmacokinetics

The nivolumab and ipilimumab concentration vs time data obtained in this study will be combined with data from other studies in the clinical development program to develop a population PK model. This model will be used to evaluate the effects of intrinsic and extrinsic covariates on the PK of nivolumab and ipilimumab to determine measures of individual exposure (such as steady state peak, trough and time-averaged concentration). Pharmacokinetic drug- drug interaction between nivolumab and ipilimumab will be studied by population PK approach as appropriate. Model determined exposures may be used for exposure-response analyses of selected efficacy and safety endpoints. The results of population PK, pharmacokinetic drug interaction and exposure response analyses will be reported separately, as needed.

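### Protocol Table 5.5.1-1 times the ipilimumab end-of-infusion sample at 00:30 on the nivolumab clock, about 30 minutes before ipilimumab starts; the table's own footnote d puts it at about 85-88 minutes

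*Protocol*

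**What the plan says.** Protocol Table 5.5.1-1 gives the PK and immunogenicity sampling times. Its single time column is headed "Time (Relative to Start of Nivolumab Infusion) Hours:Min". On C1D1, C2D1 and C3D1 it lists the nivolumab end-of-infusion sample (EOI-nivo) at 00:90 and the ipilimumab one (EOI-ipi) at 00:30. On C5D1, when nivolumab is given alone, EOI-nivo is at 00:30. All predose samples are at 00:00.

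Three other statements bear on these times:

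- Protocol section 5.5, which refers to this table for sample collection, says: "All timepoints are relative to the start of study drug administration".
- Protocol section 4.3.1 fixes the order ("nivolumab is to be administered first") and the nivolumab duration ("Subjects should receive nivolumab at a dose of 3 mg/kg (Arm A) or 1 mg/kg (Arm B) as a 30-minute IV infusion"). It says the ipilimumab infusion "will start approximately 30 minutes after completion of the nivolumab infusion", and gives ipilimumab 30 minutes as well.
- Footnote d to the table, attached to every end-of-infusion row, says that for sequential dosing "both EOI samples should be collected immediately (preferably within 2 - 5 minutes) prior to the end of the ipilimumab infusion".

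SAP section 7.7 puts the concentration data into a population PK model that derives individual exposure, including peak. It adds: "Model determined exposures may be used for exposure-response analyses of selected efficacy and safety endpoints".

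**The concern.** On the clock named in the heading, an ipilimumab end-of-infusion sample at 30 minutes falls as nivolumab finishes and before any ipilimumab has been given that day. Footnote d, on the same rows, asks for a draw close to an hour later. The cell and its footnote cannot both be followed.

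A site that goes by the row label and the footnote obtains a valid near-peak sample. A site that goes by the clock time would collect serum with no study ipilimumab in Cycle 1, and with a predose level in Cycles 2 and 3, in each case labelled as end of infusion. Those values would enter the population PK model as ipilimumab peaks. The arms differ in ipilimumab dose (1 mg/kg against 3 mg/kg), so ipilimumab exposure is relevant to any later exposure-response work.

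**Working it through.** **Inputs** (minutes; all from the Protocol)

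- Nivolumab infusion: 30 (section 4.3.1)
- Gap before ipilimumab: g, about 30 (section 4.3.1)
- Ipilimumab infusion: 30 (section 4.3.1)
- Draw: 2 to 5 before the end of ipilimumab (footnote d)
- Table entries in C1-C3: EOI-nivo 00:90, EOI-ipi 00:30
- Zero of the clock: start of nivolumab (column heading)

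**Timeline on the stated clock**

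- Ipilimumab start = 30 + 30 = 60
- Ipilimumab end = 60 + 30 = 90
- Footnote d window = 90 - 5 to 90 - 2 = 85 to 88

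**Each kind of entry against the timeline**

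| Entry | Listed | Derived | Result |
|---|---|---|---|
| Predose | 0 | 0 | fits |
| EOI-nivo, C1-C3 | 90 | 85-88, nominally 90 | fits |
| EOI-nivo, C5 (nivolumab alone, 30-minute infusion, section 4.3.2) | 30 | 30 | fits |
| EOI-ipi, C1-C3 | 30 | 85-88, nominally 90 | does not fit |

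Size of the mismatch:

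- Against the start of ipilimumab: 60 - 30 = 30 minutes too early.
- Against the footnote d draw: 85 - 30 = 55 to 88 - 30 = 58 minutes too early.

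**Does the word approximately rescue it?** For any gap g, the window is 30 + g + 30 - 5 to 30 + g + 30 - 2, that is 55 + g to 58 + g. With g = 0 it is 55-58, and with g = 45 it is 100-103. A window containing 30 would need g between -28 and -25, which means starting ipilimumab while nivolumab is still running. No sequential schedule gives 30.

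**Which clock would give 00:30?** Counted from the start of ipilimumab, the infusion ends at 30 and the footnote d draw is at 25-28. On the nivolumab clock, 30 minutes after the start of ipilimumab is 60 + 30 = 90, the same moment as EOI-nivo. The likely origin is therefore a second clock used in the same column without being named.

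**Were the two values swapped?** Then EOI-ipi would be 00:90, as derived above, but EOI-nivo would be 00:30 and would contradict footnote d, which sets both draws at the end of ipilimumab. The table would still need correcting.

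**Share of ipilimumab PK samples.** The table schedules 4 predose samples (C1, C2, C3, C5) and 3 end-of-infusion samples (C1, C2, C3), 7 in all. The affected ones are 3 of 7, and the other 4 are all predose.

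**The case against.** The best defence is that the numbers are sound and only the heading is incomplete. If each drug is timed from its own start, 00:90 for nivolumab and 00:30 for ipilimumab are the same moment and agree with footnote d. Section 5.5 refers to the start of study drug, and section 4.1 lists both agents as investigational products, so that sentence can be read drug by drug. Footnote d is also tied to the event: it moves the draw if the end of infusion is delayed. The harm requires staff to take an ipilimumab end-of-infusion sample before hanging ipilimumab, against both the row label and the footnote. Finally, SAP section 7.4.1 computes infusion duration from recorded start and stop times for both drugs, so a wrong nominal time could be corrected in analysis.

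Much of this stands. The section 5.5 sentence is open to a per-drug reading, so the finding should rest on the column heading. Footnote d is workable and lowers the practical risk. Protocol section 8.4.5 is redacted and the laboratory manual is not available, so nothing can be inferred from silence about actual sampling times.

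The heading, however, is explicit: it names nivolumab as the zero and makes no exception for the EOI-ipi rows. No text ranks the footnote above the cell. Recorded times could repair a wrong label, but they could not recover a near-peak sample that was drawn before the drug was given.

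**Conclusion.** The concern holds. Three cells of an operative sampling schedule are wrong as written. On the stated clock they fall about 30 minutes before ipilimumab starts and 55-58 minutes before the draw that footnote d describes.

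These figures assume the section 4.3.1 durations and a gap of 30 minutes. The exact minutes move with the gap, but the contradiction remains at any gap of zero or more. That 00:30 was counted from the start of ipilimumab is the most plausible explanation, not something the documents state.

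The reach is limited to the PK work: at most 3 of 7 ipilimumab PK samples per subject, though these are the only ones scheduled near peak. The documents do not show how many sites would follow the clock time, so no number of mistimed samples can be given. The primary endpoint, power, ORR, PFS and OS are unaffected. The point is worth correcting because it is certain and cheap to fix, not because it threatens the main conclusions.

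**What to change.** Reconcile the three EOI-ipi cells (C1D1, C2D1, C3D1) with the column heading and footnote d, in one of two ways:

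- change them to about 00:90 from the start of nivolumab; or
- keep 00:30 and state in the heading or a footnote that the EOI-ipi rows count from the start of ipilimumab.

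Send sites a short note that both end-of-infusion samples are taken just before ipilimumab ends. As a useful extra, confirm in the laboratory manual or PK data specification that the PK dataset uses actual sampling and infusion times for both drugs.

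The cost is three table cells or one note, plus the message to sites. No sample is added, and nothing changes in dosing or in the statistical analysis.
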